## **12.10 Quality Assurance and Quality Control**

Each clinical site will perform internal quality management of study conduct, data and biological specimen collection, documentation, and completion. An individualized quality management plan will be developed to describe a site's quality management.

Quality control (QC) procedures will be implemented beginning with the data entry system and at each stage of data handling. Any missing data or data anomalies will be communicated to the site(s) for clarification/resolution.

The Sponsor (or designated CRO) is responsible for implementing and maintaining quality assurance (QA) and QC systems with written SOPs. In accordance with the written SOPs, monitors will verify that the clinical trial is conducted, data are generated, and biological specimens are collected, recorded, and reported in compliance with the protocol, ICH GCP, and applicable regulatory requirements (e.g., GLP, Good Manufacturing Practice [GMP]). The Sponsor and monitor will determine the frequency of monitoring visits.

During the study, the Sponsor may conduct audits separately from routine monitoring. The investigational site will provide direct access to all trial-related sites, source data/documents, and reports for routine monitoring and/or auditing by the Sponsor, and inspection by local and regulatory authorities.

## **12.11 Protocol Deviations and GCP Non-Compliance**

A protocol deviation is any noncompliance to the clinical trial protocol and non-compliance with ICH/GCP; both will be monitored and reported as per local regulations. The non-compliance may be on the part of the patient, the Investigator, or the study site/CRO staff. Protocol deviations must be documented, and corrective actions have to be developed and implemented promptly.

It is the responsibility of the site Investigator to use continuous vigilance to identify and report deviations timely. All deviations must be addressed in study source documents and reported to the monitor and/or Sponsor. Protocol deviations must be sent to the reviewing IRB per their policies. The site Investigator is responsible for knowing and adhering to the reviewing IRB requirements.

For protocol deviations deemed to have no influence on the interpretation of study results, the level and reason of deviation or delay will be accurately described and comprehensively considered by the Investigator, Sponsor, monitor, or statistician.

Protocol waivers are not permitted. Neither CRO nor Sponsor approves of protocol waivers, as per GCP and regulatory guidelines. All major protocol deviations should be listed in the Clinical Study Report.

## **12.12 Publication and Data Sharing Policy**

The data generated by this study are the proprietary information of the Sponsor. Public disclosure of study data may include publication in a peer-reviewed journal.

## **12.13 Conflict of Interest Policy**

Actual or perceived conflict of interest of persons who have a role in the design, conduct, analysis, publication, or any aspect of this trial will be disclosed and managed.

## **12.14 Abbreviations**

ADSP	Adaptive Study Design Plan
AE	Adverse Event
AESI	Adverse Event of Special Interest
ANC	Absolute Neutrophil Count
ATP	Adenosine Triphosphate
AUC	Area Under the Concentration-Time Curve
[REDACTED]	[REDACTED]
[REDACTED]	[REDACTED]
CFR	Code Of Federal Regulations
CI	Confidence Interval
C max	Peak Concentration
CR	Complete Response
CRO	Contract Research Organization
CT	Computerized Tomography
CTCAE	Common Terminology Criteria for Adverse Event
[REDACTED]	[REDACTED]
DLT	Dose Limiting Toxicity
DoR	Duration of Response
ECG	Electrocardiogram
ECOG	Eastern Cooperative Oncology Group
eCRF	Electronic Case Report Form
EF	Ejection Fraction
EGFR	Epidermal Growth Factor Receptor
EOT	End of Treatment
EWOC	Escalation with Overdose Control

FDA	Food and Drug Administration
FSH	Follicle Stimulating Hormone
GCP	Good Clinical Practice
GLP	Good Laboratory Practice
GMP	Good Manufacturing Practice
HED	Human Equivalent Dose
HIV	Human Immunodeficiency Virus
HNSTD	Highest Non-Severely Toxic Dose
ICF	Informed Consent Form
ICH	International Conference on Harmonisation
ILD	Interstitial Lung Disease
IND	Investigational New Drug
IRB	Institutional Review Board
IV	Intravenous(ly)
IWRS	Interactive Web Response System
LH	Luteinizing Hormone
MedDRA	Medical Dictionary for Drug Regulatory Activities
MRI	Magnetic Resonance Imaging
MTD	Maximum Tolerated Dose
MTPI-2	Modified Toxicity Probability Interval-2
MUGA	Multi-gated Acquisition
NOAEL	No Observed Adverse Effect Level
NSCLC	Non-Small Cell Lung Cancer
ORR	Objective Response Rate
PBPK	Physiologically Based PK
PD	Progressive Disease
PFS	Progression-Free Survival
PI	Principal Investigator
PK	Pharmacokinetics
PP	Per Protocol
PR	Partial Response
PSA	Prostate Specific Antigen
QA	Quality Assurance
QC	Quality Control
QD	Once daily
QTc	corrected QT Interval
QTcF	QT Interval Corrected Using Fridericia's Formula
RECIST	Response Evaluation Criteria In Solid Tumors
RP2D	Recommended Phase 2 Dose
SAE	Serious Adverse Event
SD	Stable Disease
SMC	Safety Monitoring Committee
SoA	Schedule of Activities

---

SOP	Standard Operating Procedure
STD	Severely Toxic Dose
T 1/2	Half-life
TKI	Tyrosine Kinase Inhibitor
T max	Time to Peak Concentration
ULN	Upper Limit of Normal
WHO	World Health Organization

## 12.15 Protocol Amendment History

Version	Date	Description of Change	Brief Rationale

Version	Date	Description of Change	Brief Rationale
V2.0			

[figure not shown]

Version	Date	Description of Change	Brief Rationale

The figure consists of a 3x3 grid of 9 horizontal bar charts. Each chart is composed of two bars: a black bar on the left and a white bar on the right. The length of the black bar varies across the charts, indicating different values for each row and column. The grid is defined by three horizontal and three vertical lines, creating a 4x4 grid of cells. The bars are positioned such that they overlap the grid lines, with the black bar extending from the left edge of the grid to the right edge of the black bar in the adjacent cell, and the white bar extending from the right edge of the black bar in the adjacent cell to the right edge of the grid.

[figure not shown]
[figure not shown]
[figure not shown]
This diagram illustrates a 2D convolution operation with a stride of 2. The input layer (rows 0-3) consists of 16 units arranged in a 4x4 grid. The hidden layer (rows 4-7) consists of 4 units arranged in a 2x2 grid. The output layer (rows 8-9) consists of 1 unit. The diagram shows the receptive fields of each output unit, which are shaded in black. The first column represents the input units, and the second column represents the hidden layer units. The output layer is a single unit.

The figure consists of a 3x3 grid of horizontal bar charts. Each chart has a black background and white text. The top row has 10 bars, the middle row has 10 bars, and the bottom row has 10 bars. Each bar is black and has a different length, representing data values for each category in each row.

Version	Date	Description of Change	Brief Rationale
1.0	2024-01-01	Initial release of the system.	System is now operational.
1.1	2024-01-15	Minor bug fix for reporting module.	Addressed a critical bug in the reporting module.

The figure consists of a 4x4 grid of 16 black bars. The bars are arranged in four rows and four columns. The total length of bars in each row and column is constant, creating a stepped, pyramid-like visual effect. The bars are positioned such that the total length of bars in each row and column is constant, creating a stepped, pyramid-like visual effect.

The figure consists of a 5x5 grid of horizontal bars. Each bar is composed of a black segment and a white segment. The bars are arranged in a staggered pattern, creating a visual effect of depth or movement. The lengths of the bars vary, with some being longer and others shorter, adding to the complexity of the pattern. The overall effect is a high-contrast, abstract graphic design.

The figure consists of a 5x5 grid of 25 black bars. The bars are arranged in a staggered, non-overlapping manner. The lengths of the bars vary significantly, with some being very long and others very short. The grid is bounded by a thin black border.

The figure consists of a 4x4 grid of 16 smaller bar charts. Each chart has a vertical y-axis on the left and a horizontal x-axis at the bottom. The bars are solid black. The charts are arranged in a 4x4 grid. The first three rows have 8 bars each, and the fourth row has 4 bars.

## 14 APPENDICES

Appendix 1. Signature of Investigator

Appendix 2. Eastern Cooperative Oncology Group (ECOG) Performance Status

Appendix 3. Response Evaluation Criteria in Solid Tumors (RECIST Version 1.1)

Appendix 4. List of CYP3A4 Substrates With Narrow Therapeutic Index, CYP2C8 Strong Inhibitor, and P-gp Inhibitor

**Appendix 5. Decision rules for dose escalation derived from the modified toxicity probability interval-2 (mTPI-2) method**

---

## Appendix 2. Eastern Cooperative Oncology Group (ECOG) Performance Status

### Grade      Description

0	Fully active, able to carry on all pre-disease performance without restriction
1	Restricted in physically strenuous activity but ambulatory and able to carry out work of a light or sedentary nature, e.g., light house work, office work
2	Ambulatory and capable of all self-care but unable to carry out any work activities. Up and about more than 50% of waking hours
3	Capable of only limited self-care, confined to bed or chair more than 50% of waking hours
4	Completely disabled. Cannot carry on any self-care. Totally confined to bed or chair
5	Dead

Source: Oken MM, Creech RH, Tormey DC, Horton J, Davis TE, McFadden ET, et al. Toxicity and response criteria of the Eastern Cooperative Oncology Group. Am J Clin Oncol.1982;5:649-55.

### Appendix 3. Response Evaluation Criteria in Solid Tumors (RECIST Version 1.1)

The text below was obtained from the following reference:

#### DEFINITIONS

Response and progression will be evaluated in this trial using the international criteria proposed by the Response Evaluation Criteria in Solid Tumors (RECIST) Committee (version 1.1). Changes in only the largest diameter (uni-dimensional measurement) of the tumor lesions are used in the RECIST criteria.

Note: Lesions are either measurable or non-measurable using the criteria provided below. The term “evaluable” in reference to measurability will not be used because it does not provide additional meaning or accuracy.

#### Measurable Disease

Tumor lesions: Must be accurately measured in at least 1 dimension (longest diameter in the plane of measurement is to be recorded) with a minimum size of:

- 10 mm by CT scan (irrespective of scanner type) and MRI (no less than double the slice thickness and a minimum of 10 mm).
- 20 mm by chest X ray (if clearly defined and surrounded by aerated lung).

Malignant lymph nodes: To be considered pathologically enlarged and measurable, a lymph node must be  $\geq 15$  mm in short axis when assessed by CT scan (CT scan slice thickness recommended to be no greater than 5 mm). At baseline and in follow up, only the short axis will be measured and followed.

#### Non-measurable Disease

All other lesions (or sites of disease), including small lesions (longest diameter  $\geq 10$  to  $< 15$  mm with conventional techniques or  $< 10$  mm using spiral CT scan), are considered non-measurable disease.

Leptomeningeal disease, ascites, pleural, or pericardial effusion, inflammatory breast disease, lymphangitic involvement of skin or lung, abdominal masses/abdominal organomegaly identified by physical examination that is not measurable by reproducible imaging techniques are all non-measurable.

Bone lesions:

- Bone scan, PET scan, or plain films are not considered adequate imaging techniques to measure bone lesions. However, these techniques can be used to confirm the presence or disappearance of bone lesions
- Lytic bone lesions or mixed lytic-blastic lesions, with identifiable soft tissue components, that can be evaluated by cross sectional imaging techniques such as CT or MRI can be considered as measurable lesions if the soft tissue component meets the definition of measurability described above.
- Blastic bone lesions are non-measurable.

Cystic lesions:

- Lesions that meet the criteria for radiographically defined simple cysts should not be considered as malignant lesions (neither measurable nor non measurable) since they are, by definition, simple cysts.
- ‘Cystic lesions’ thought to represent cystic metastases can be considered as measurable lesions, if they meet the definition of measurability described above. However, if non cystic lesions are present in the same patient, these are preferred for selection as target lesions.

Lesions with prior local treatment:

- Tumor lesions situated in a previously irradiated area, or in an area subjected to other locoregional therapy, are usually not considered measurable unless there has been demonstrated progression in the lesion. Trial protocols should detail the conditions under which such lesions would be considered measurable.

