## 7 STUDY POPULATION

### 7.1 Inclusion Criteria

For inclusion in the study, patients must fulfill all of the following criteria:

1. Provision of signed and dated, written informed consent before any study specific procedures, sampling and analyses
2. Aged at least 18 years
3. Histological or cytological confirmation of advanced and/or metastatic stage IIIB/IV NSCLC
4. Radiological documentation of disease progression while on a previous continuous (at least 30 days) treatment with an EGFR TKI monotherapy (including, but not limited to, osimertinib, afatinib, dacomitinib, gefitinib, or erlotinib). All patients must have documented radiological progression on the last treatment administered prior to enrolling in the study
5. [REDACTED]

[REDACTED]  
[REDACTED]  
[REDACTED]  
[REDACTED]

World Health Organization  
(WHO) criteria, after treatment of an EGFR TKI

6. Adequate bone marrow reserve or organ function as demonstrated by all of the following laboratory values:
  - Absolute neutrophil count (ANC)  $> 1.5 \times 10^9$  cells/L (without growth factor support for 2 weeks prior to testing)
  - Platelet count  $> 75 \times 10^9$  cells/L (without transfusion or growth factor support for 1 week prior to testing)
  - Hemoglobin  $> 9.0$  g/dL (without transfusion or growth factor support for 2 weeks prior to testing)
  - Alanine aminotransferase  $\leq 2.5$  times the upper limit of normal (ULN)
  - Aspartate aminotransferase  $\leq 2.5$  times the ULN
  - Total bilirubin  $\leq 1.5$  times the ULN

- Creatinine  $\leq$ 1.5 times the ULN, creatinine clearance  $\geq$ 50 mL/min (measured or calculated by Cockcroft-Gault equation). Confirmation of creatinine clearance is required when creatinine is  $>$  1.5 times the ULN

7.

[REDACTED]

8. Patients must have measurable disease per RECIST v1.1 presented
9. Eastern Cooperative Oncology Group (ECOG) performance status of 0 to 1
10. Females, if of child-bearing potential, should be using adequate contraceptive measures, should not be breastfeeding, and must have a negative pregnancy test result prior to start of dosing, or must have evidence of non-child-bearing potential by fulfilling one of the following criteria at Screening:
  - Post-menopausal defined as aged more than 50 years and amenorrhoeic for at least 12 months following cessation of all exogenous hormonal treatments

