### **Target Lesions**

All measurable lesions up to a maximum of 2 lesions per organ and 5 lesions in total, should be identified as target lesions and recorded and measured at baseline. Target lesions should be selected on the basis of their size (lesions with the longest diameter), be representative of all involved organ, but in addition should be those that lend themselves to reproducible repeated measurements.

Lymph nodes merit special mention since they are normal anatomical structures which may be visible by imaging even if not involved by tumor. Pathological nodes which are defined as measurable and may be identified as target lesions must meet the criterion of a short axis of  $\geq 15$  mm by CT scan. Only the short axis of these nodes will contribute to the baseline sum. The short axis of the node is the diameter normally used by radiologists to judge if a node is involved by solid tumor. Nodal size is normally reported as 2 dimensions in the plane in which the image is obtained (for CT scan this is almost always the axial plane; for MRI the plane of acquisition may be axial, sagittal, or coronal). The smaller of these measures is the short axis. For example, an abdominal node which is reported as being 20 mm  $\times$  30 mm has a short axis of 20 mm and qualifies as a malignant, measurable node. In this example, 20 mm should be recorded as the node measurement. All other pathological nodes (those with short axis  $\geq 10$  mm but  $< 15$  mm) should be considered non target lesions. Nodes that have a short axis  $< 10$  mm are considered non pathological and should not be recorded or followed.

A sum of the diameters (longest for non-nodal lesions, short axis for nodal lesions) for all target lesions will be calculated and reported as the baseline sum diameters. If lymph nodes are to be included in the sum, then as noted above, only the short axis is added into the sum. The baseline sum diameters will be used as reference to further characterize any objective tumor regression in the measurable dimension of the disease.

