APPENDIX 2. RESPONSE EVALUATION CRITERIA IN SOLID TUMORS (RECIST VERSION 1.1)

The text below was obtained from the following reference:

DEFINITIONS

Response and progression will be evaluated in this trial using the international criteria proposed by the Response Evaluation Criteria in Solid Tumors (RECIST) Committee (version 1.1). Changes in only the largest diameter (uni-dimensional measurement) of the tumor lesions are used in the RECIST criteria. Note: Lesions are either measurable or non-measurable using the criteria provided below. The term “evaluable” in reference to measurability will not be used because it does not provide additional meaning or accuracy.

Measurable Disease

Tumor lesions: Must be accurately measured in at least 1 dimension (longest diameter in the plane of measurement is to be recorded) with a minimum size of:

- 10 mm by CT scan (irrespective of scanner type) and MRI (no less than double the slice thickness and a minimum of 10 mm).
- 20 mm by chest X ray (if clearly defined and surrounded by aerated lung).

Malignant lymph nodes: To be considered pathologically enlarged and measurable, a lymph node must be ≥ 15 mm in short axis when assessed by CT scan (CT scan slice thickness recommended to be no greater than 5 mm). At baseline and in follow up, only the short axis will be measured and followed.

Non-measurable Disease

All other lesions (or sites of disease), including small lesions (longest diameter ≥ 10 to < 15 mm with conventional techniques or < 10 mm using spiral CT scan), are considered non-measurable disease. Leptomeningeal disease, ascites, pleural, or pericardial effusion, inflammatory breast disease, lymphangitic involvement of skin or lung, abdominal masses/abdominal organomegaly identified by physical examination that is not measurable by reproducible imaging techniques are all non-measurable.

Bone lesions:

- Bone scan, PET scan, or plain films are not considered adequate imaging techniques to measure bone lesions. However, these techniques can be used to confirm the presence or disappearance of bone lesions

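### The RECIST appendices contradict themselves on whether a non-nodal lesion of 10 to <15 mm seen on thin-slice non-spiral CT (and possibly MRI) is measurable; low severity

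*Protocol*

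**What the plan says.** Protocol Appendix 3 sets out a two-way classification: "Lesions are either measurable or non-measurable using the criteria provided below".

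- **Measurable Disease.** For non-nodal tumor lesions the minimum longest diameter is "10 mm by CT scan (irrespective of scanner type) and MRI (no less than double the slice thickness and a minimum of 10 mm"). For plain films it is "20 mm by chest X ray (if clearly defined and surrounded by aerated lung"). Lymph nodes need a short axis of at least 15 mm.
- **Non-measurable Disease.** This covers every other lesion and gives small lesions as an example. The bracket sets two bands of longest diameter: 10 to <15 mm with conventional techniques, and below 10 mm with spiral CT. It ends "mm using spiral CT scan), are considered non-measurable disease".
- **Target Lesions.** Target lesions are drawn from the measurable ones. Pathological nodes with a short axis of 10 to <15 mm "should be considered non target lesions".
- **CT, MRI paragraph.** Where CT slices exceed 5 mm, the minimum measurable size is twice the slice thickness.

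SAP Appendix 2 carries the same text, including "with conventional techniques or < 10 mm using spiral CT scan), are considered non-measurable disease".

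The classification is used in Protocol 7.1, criterion 8: "Patients must have measurable disease per RECIST v1.1 presented". Under Protocol 10.1.1 the investigator chooses the imaging modality, and the local reading decides eligibility.

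**The concern.** The Measurable Disease line says that the type of CT scanner does not matter. The bracket in the next subsection makes it matter: it keeps the 10 mm cut-off for spiral CT only and excludes a further 5 mm band for conventional techniques. A lesion in that band cannot be both measurable and non-measurable, and the appendix allows no third class.

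The classification decides whether a patient with only such lesions can enter. In other patients it decides whether such a lesion goes into the baseline sum or is followed as non-target, without measurement. Partial response is a 30% fall in that sum. ORR is the primary endpoint of Part 2 and a secondary endpoint of Part 1, and SAP 7.1.1 builds response from the investigator's target-lesion assessments. Two sites could therefore handle the same scan differently, each following the text.

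**Working it through.** No sample size, power or error rate is involved, so the check is a comparison of thresholds. The question in each row is how a lesion of 10 to <15 mm is classed.

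| Lesion and technique | Measurable Disease, Target Lesions and CT, MRI text | Non-measurable bracket | Agree? |
|---|---|---|---|
| Non-nodal, spiral CT, slices ≤5 mm | measurable (≥10 mm) | not excluded (cut-off <10 mm) | yes |
| Non-nodal, non-spiral CT, slices ≤5 mm | measurable (≥10 mm, any scanner) | non-measurable | **no** |
| Non-nodal, MRI, at least twice the slice thickness | measurable (≥10 mm) | non-measurable if MRI is a conventional technique | **no, on that condition** |
| Non-nodal, chest X-ray | non-measurable (minimum 20 mm) | non-measurable | yes |
| Lymph node, short axis | not measurable (minimum 15 mm); non-target | not addressed (bracket uses longest diameter) | yes |

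**Effect of slice thickness on the non-spiral CT row.** For slice thickness t, the contradictory band runs from max(10, 2t) mm to <15 mm.

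- t = 5 mm: max(10, 10) = 10, so the band is 10 to <15 mm.
- t = 6 mm: max(10, 12) = 12, so the band is 12 to <15 mm.
- t = 7.5 mm: max(10, 15) = 15, so no band is left.

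The conflict is therefore widest for slices of 5 mm or less and disappears at 7.5 mm and above.

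**How a response category could change.** The sizes here are invented for illustration. A patient has one lesion that shrinks from 40 to 30 mm and another that shrinks from 12 to 6 mm, the second in the disputed band.

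- Both are targets: the sum falls from 40 + 12 = 52 mm to 30 + 6 = 36 mm. The change is (36 − 52)/52 = −31%, which meets the PR criterion.
- The 12 mm lesion is non-target: the sum falls from 40 to 30 mm. The change is (30 − 40)/40 = −25%, which is SD.

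This shows that the mechanism is real. It does not show how often it would operate.

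**The case against.** The strongest reply is that the non-measurable class is residual: it opens by covering all other lesions, so a 12 mm CT lesion is already measurable before that subsection applies, and the bracket is only a poorly worded example. This softens the clash but does not remove it. The example names a lesion that the preceding subsection has just called measurable, and a reader who consults only that line gets the opposite answer.

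A second reply is that sites will use spiral CT, where the lines agree. That may well be so in practice, but nothing in the visible text requires it, and part of the imaging section is redacted. MRI readings are foreseeable too: brain MRI is mandatory at screening, and exclusion criterion 3 admits asymptomatic, stable brain metastases that meet its conditions.

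Third, the consequence is limited, and this stands. Eligibility changes only if the patient has no undisputed measurable lesion. Target lesions are chosen with size as a main criterion, so larger lesions tend to come first and the disputed lesion matters mainly where there are few of them.

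A reader might infer more than the documents support in three ways:

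- That every CT or MRI lesion of 10 to <15 mm is affected. Spiral CT is not, the slice-thickness rule narrows the CT band, and MRI depends on an undefined term.
- That an effect on the Part 2 ORR can be sized from the 12 and 30 patients in Protocol 12.8. Those describe the Part 1 RP2D exploratory cohorts, as a committee review point and an enrolment cap. They are not Part 2 denominators, and one patient's share of a denominator is not a shift in ORR.
- That the nodal short-axis band was transferred to longest diameters by mistake. The shared figures make this plausible, but the documents do not show how the wording arose.

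**Conclusion.** The inconsistency is real and stands in the current text of both documents. It is confined to non-nodal lesions of 10 to <15 mm on non-spiral CT with slices thinner than 7.5 mm (the full band at 5 mm or less), and on MRI if that counts as a conventional technique.

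Sites could differ on eligibility in rare cases and on baseline target sums, and hence on ORR. The size of the effect cannot be calculated: the documents give neither the share of such lesions nor the scanners in use. It is probably small, on the assumption that most sites use spiral CT with thin slices. Part 2 efficacy is descriptive, so no power or error rate is affected.

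This is an internal inconsistency of low severity. It is still worth correcting, because the rule governs entry and the measurement behind the primary endpoint of Part 2.

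**What to change.** Reconcile the Non-measurable Disease subsection in Protocol Appendix 3, and its copy in SAP Appendix 2, with the Measurable Disease, Target Lesions and CT, MRI text of the same appendices. One wording that would do this in place of the present bracketed example:

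*small lesions below the minimum sizes given above (longest diameter <10 mm, or less than twice the slice thickness where that is larger, on CT/MRI; <20 mm on chest X-ray) and pathological lymph nodes with short axis 10 to <15 mm*

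This drops the undefined reference to conventional techniques, keeps the slice-thickness condition and puts the 10 to <15 mm band where Target Lesions already uses it.

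The cost is one bracket in each document: a clarification letter or the next amendment for the protocol, and a matching wording correction in the SAP. The analysis methods do not change. If patients have already been enrolled, the sponsor could ask sites whether any target or excluded lesion fell in the disputed band.
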